Appendix 4 **ECOG Performance Status Scale**

Grade	Description
0	Fully active, able to carry on all pre-disease performance without restriction
1	Restricted in physically strenuous activity but ambulatory and able to carry out work of a light or sedentary nature, e.g., light housework or office work
2	Ambulatory and capable of all self-care but unable to carry out any work activities. Up and about > 50% of waking hours
3	Capable of only limited self-care, confined to a bed or chair > 50% of waking hours
4	Completely disabled. Cannot carry on any self-care. Totally confined to bed or chair
5	Dead

Appendix 5 **Response Evaluation Criteria in Solid Tumors, Version 1.1** **(RECIST v1.1)**

Selected sections from the Response Evaluation Criteria in Solid Tumors, Version 1.1 (RECIST v1.1), (Eisenhauer et al. 2009) are presented below, with slight modifications from the original publication and the addition of explanatory text as needed for clarity.¹

TUMOR MEASURABILITY

At baseline, tumor lesions/lymph nodes will be categorized as measurable or non-measurable as described below. All measurable and non-measurable lesions should be assessed at screening and at subsequent protocol-specified tumor assessment timepoints. Additional assessments may be performed as clinically indicated for suspicion of progression.

DEFINITION OF MEASURABLE LESIONS

Tumor Lesions

Tumor lesions must be accurately measured in at least one dimension (longest diameter in the plane of measurement is to be recorded) with a minimum size as follows:

- 10 mm by computed tomography (CT) or magnetic resonance imaging (MRI) scan (CT/MRI scan slice thickness/interval \leq 5 mm)
- 10-mm caliper measurement by clinical examination (lesions that cannot be accurately measured with calipers should be recorded as non-measurable)
- 20 mm by chest X-ray

Malignant Lymph Nodes

To be considered pathologically enlarged and measurable, a lymph node must be \geq 15 mm in the short axis when assessed by CT scan (CT scan slice thickness recommended to be \leq 5 mm). At baseline and follow-up, only the short axis will be measured and followed. Additional information on lymph node measurement is provided below (see "Identification of Target and Non-Target Lesions" and "Calculation of Sum of Diameters").

¹ For clarity and for consistency within this document, the section numbers and cross-references to other sections within the article have been deleted and minor changes have been made.

Appendix 5Response Evaluation Criteria in Solid Tumors, Version 1.1 (RECIST v1.1)

DEFINITION OF NON-MEASURABLE LESIONS

Non-measurable tumor lesions encompass small lesions (longest diameter < 10 mm or pathological lymph nodes with short axis \geq 10 mm but < 15 mm) as well as truly non-measurable lesions. Lesions considered truly non-measurable include leptomeningeal disease, ascites, pleural or pericardial effusion, inflammatory breast disease, lymphangitic involvement of skin or lung, peritoneal spread, and abdominal mass/abdominal organomegaly identified by physical examination that is not measurable by reproducible imaging techniques.

SPECIAL CONSIDERATIONS REGARDING LESION MEASURABILITY

Bone lesions, cystic lesions, and lesions previously treated with local therapy require particular comment, as outlined below.

Bone Lesions:

- Technetium-99m bone scans, sodium fluoride positron emission tomography scans, and plain films are not considered adequate imaging techniques for measuring bone lesions. However, these techniques can be used to confirm the presence or disappearance of bone lesions.
- Lytic bone lesions or mixed lytic-blastic lesions with identifiable soft tissue components that can be evaluated by cross-sectional imaging techniques such as CT or MRI can be considered measurable lesions if the soft tissue component meets the definition of measurability described above.
- Blastic bone lesions are non-measurable.

Cystic Lesions:

- Lesions that meet the criteria for radiographically defined simple cysts should not be considered malignant lesions (neither measurable nor non-measurable) since they are, by definition, simple cysts.
- Cystic lesions thought to represent cystic metastases can be considered measurable lesions if they meet the definition of measurability described above. However, if non-cystic lesions are present in the same patient, these are preferred for selection as target lesions.

METHODS FOR ASSESSING LESIONS

All measurements should be recorded in metric notation, using calipers if clinically assessed. All baseline evaluations should be performed as close as possible to the treatment start and never more than four weeks before the beginning of the treatment.

The same method of assessment and the same technique should be used to characterize each identified and reported lesion at baseline and during the study. Imaging-based evaluation should always be the preferred option.

Appendix 5Response Evaluation Criteria in Solid Tumors, Version 1.1 (RECIST v1.1)

CLINICAL LESIONS

Clinical lesions will only be considered measurable when they are superficial and ≥ 10 mm in diameter as assessed using calipers (e.g., skin nodules). For the case of skin lesions, documentation by color photography, including a ruler to estimate the size of the lesion, is suggested.

CHEST X-RAY

Chest CT is preferred over chest X-ray, particularly when progression is an important endpoint, since CT is more sensitive than X-ray, particularly in identifying new lesions. However, lesions on chest X-ray may be considered measurable if they are clearly defined and surrounded by aerated lung.

CT AND MRI SCANS

CT is the best currently available and reproducible method to measure lesions selected for response assessment. In this guideline, the definition of measurability of lesions on CT scan is based on the assumption that CT slice thickness is ≤ 5 mm. When CT scans have slice thickness of > 5 mm, the minimum size for a measurable lesion should be twice the slice thickness. MRI is also acceptable.

If prior to enrollment it is known that a patient is unable to undergo CT scans with IV contrast because of allergy or renal insufficiency, the decision as to whether a non-contrast CT or MRI (without IV contrast) will be used to evaluate the patient at baseline and during the study should be guided by the tumor type under investigation and the anatomic location of the disease. For patients who develop contraindications to contrast after baseline contrast CT is done, the decision as to whether non-contrast CT or MRI (enhanced or non-enhanced) will be performed should also be based on the tumor type and the anatomic location of the disease, and should be optimized to allow for comparison with the prior studies if possible. Each case should be discussed with the radiologist to determine if substitution of these other approaches is possible and, if not, the patient should be considered not evaluable from that point forward. Care must be taken in measurement of target lesions and interpretation of non-target disease or new lesions on a different modality, since the same lesion may appear to have a different size using a new modality.

ENDOSCOPY, LAPAROSCOPY, ULTRASOUND, TUMOR MARKERS, CYTOLOGY, HISTOLOGY

Endoscopy, laparoscopy, ultrasound, tumor markers, cytology, and histology cannot be used for objective tumor evaluation.

ASSESSMENT OF TUMOR BURDEN

To assess objective response or future progression, it is necessary to estimate the overall tumor burden at baseline and use this as a comparator for subsequent measurements.

Cobimetinib, atezolizumab, vemurafenib — F. Hoffmann-La Roche Ltd

154 / Protocol MO39136, Version 5.0

Appendix 5Response Evaluation Criteria in Solid Tumors, Version 1.1 (RECIST v1.1)

IDENTIFICATION OF TARGET AND NON-TARGET LESIONS

When more than one measurable lesion is present at baseline, all lesions up to a maximum of five lesions total (and a maximum of two lesions per organ) representative of all involved organs should be identified as target lesions and will be recorded and measured at baseline. This means that, for instances in which patients have only one or two organ sites involved, a maximum of two lesions (one site) and four lesions (two sites), respectively, will be recorded. Other lesions (albeit measurable) in those organs will be considered non-target lesions.

Target lesions should be selected on the basis of their size (lesions with the longest diameter) and should be representative of all involved organs, but in addition should lend themselves to reproducible repeated measurements. It may be the case that, on occasion, the largest lesion does not lend itself to reproducible measurement, in which circumstance the next largest lesion that can be measured reproducibly should be selected.

Lymph nodes merit special mention since they are normal anatomical structures that may be visible by imaging even if not involved by tumor. As noted above, pathological nodes that are defined as measurable and may be identified as target lesions must meet the criterion of a short axis of ≥ 15 mm by CT scan. Only the short axis of these nodes will contribute to the baseline sum. The short axis of the node is the diameter normally used by radiologists to judge if a node is involved by solid tumor. Lymph node size is normally reported as two dimensions in the plane in which the image is obtained (for CT, this is almost always the axial plane; for MRI, the plane of acquisition may be axial, sagittal, or coronal). The smaller of these measures is the short axis. For example, an abdominal node that is reported as being $20\text{ mm} \times 30\text{ mm}$ has a short axis of 20 mm and qualifies as a malignant, measurable node. In this example, 20 mm should be recorded as the node measurement. All other pathological nodes (those with short axis ≥ 10 mm but < 15 mm) should be considered non-target lesions. Nodes that have a short axis of < 10 mm are considered non-pathological and should not be recorded or followed.

All lesions (or sites of disease) not selected as target lesions (measurable or non-measurable), including pathological lymph nodes, should be identified as non-target lesions and should also be recorded at baseline. Measurements are not required. It is possible to record multiple non-target lesions involving the same organ as a single item on the Case Report Form (CRF) (e.g., "multiple enlarged pelvic lymph nodes" or "multiple liver metastases").

CALCULATION OF SUM OF DIAMETERS

A sum of the diameters (longest diameter for non-lymph node lesions, short axis for lymph node lesions) will be calculated for all target lesions at baseline and at each subsequent tumor assessment as a measure of tumor burden.

Appendix 5Response Evaluation Criteria in Solid Tumors, Version 1.1 (RECIST v1.1)

Measuring Lymph Nodes

Lymph nodes identified as target lesions should always have the actual short axis measurement recorded (measured in the same anatomical plane as the baseline examination), even if the node regresses to < 10 mm during the study. Thus, when lymph nodes are included as target lesions, the sum of diameters may not be zero even if complete response criteria are met, since a normal lymph node is defined as having a short axis of < 10 mm.

Measuring Lesions That Become Too Small to Measure

During the study, all target lesions (lymph node and non-lymph node) recorded at baseline should have their actual measurements recorded at each subsequent evaluation, even when very small (e.g., 2 mm). However, sometimes lesions or lymph nodes that are recorded as target lesions at baseline become so faint on CT scan that the radiologist may not feel comfortable assigning an exact measurement and may report them as being too small to measure. When this occurs, it is important that a value be recorded on the CRF, as follows:

- If it is the opinion of the radiologist that the lesion has likely disappeared, the measurement should be recorded as 0 mm.
- If the lesion is believed to be present and is faintly seen but too small to measure, a default value of 5 mm should be assigned and "too small to measure" should be ticked. (Note: It is less likely that this rule will be used for lymph nodes since they usually have a definable size when normal and are frequently surrounded by fat such as in the retroperitoneum; however, if a lymph node is believed to be present and is faintly seen but too small to measure, a default value of 5 mm should be assigned in this circumstance as well and "too small to measure" should also be ticked).

To reiterate, however, if the radiologist is able to provide an actual measurement, that should be recorded, even if it is < 5 mm, and in that case "too small to measure" should not be ticked.

Measuring Lesions That Split or Coalesce on Treatment

When non-lymph node lesions fragment, the longest diameters of the fragmented portions should be added together to calculate the sum of diameters. Similarly, as lesions coalesce, a plane between them may be maintained that would aid in obtaining maximal diameter measurements of each individual lesion. If the lesions have truly coalesced such that they are no longer separable, the vector of the longest diameter in this instance should be the maximum longest diameter for the coalesced lesion.

EVALUATION OF NON-TARGET LESIONS

Measurements are not required for non-target lesions, except that malignant lymph node non-target lesions should be monitored for reduction to < 10 mm in short axis.

Non-target lesions should be noted at baseline and should be identified as "present" or "absent" and (in rare cases) may be noted as "indicative of progression" at subsequent

Cobimetinib, atezolizumab, vemurafenib — F. Hoffmann-La Roche Ltd

156 / Protocol MO39136, Version 5.0

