3.3.7 Rationale for Biomarker Assessments

Melanoma is a heterogeneous disease driven by aberrations in cancer-related genes including BRAF and NRAS gene mutations. Differences in the genetic makeup of melanoma is likely to influence clinical response and changes in the genetic makeup give insights into potential mechanisms of acquired resistance. The aim is to characterize melanoma disease among patients, to better understand clinical responses, and to assess potential mechanisms of acquired resistance.

Tumour tissue obtained from study participants prior to study treatment initiation will be collected only if such samples are already available. It will be examined for the expression of PD-L1 protein. In addition, if sufficient tumour material is available, an analysis of cancer related genes (such as, but not limited to, BRAF and NRAS) may be performed using next-generation sequencing (NGS). The results will be analysed in relation to clinical response to identify those patients with a greater likelihood of benefiting from study treatment.

Factors in plasma hold important clues regarding the disease pathobiology of cancer patients and may serve as a surrogate for tumour tissue in cases where tissue is not easily accessible. An exploratory objective of this study is to assess biomarkers in plasma at baseline and at the time of relapse. Analysis of plasma may include the analysis of cancer related genes by performing NGS of circulating tumour DNA.

4. **MATERIALS AND METHODS**

4.1 **PATIENTS**

Approximately 60 patients with BRAF^{V600} mutation-positive melanoma patients with CNS metastases (Cohort 2) will be enrolled in this study. Enrollment has been discontinued into Cohort 1 (BRAF^{V600} wild-type cohort).

4.1.1 **Inclusion Criteria**

Patients must meet the following criteria for study entry.

Disease-specific criteria

- Histologically confirmed melanoma with radiologically confirmed brain metastases
- Documented BRAF^{V600} mutation status of melanoma tumour tissue using a validated genetic test.
- Measurable brain metastases defined as any lesion that can be accurately measured in at least one dimension as ≥ 0.5 cm by MRI. Patients who have received prior SRT or surgery for brain metastases must have untreated brain lesions that can be accurately measured in at least one dimension as ≥ 0.5 cm by MRI.
- Prior anti-cancer therapy for metastatic melanoma is allowed, with the following exceptions:

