Intracranial disease must be followed by MRI. Extracranial tumour assessments will include contrast-enhanced CT or MRI scans of the chest, abdomen and pelvis. Imaging of the neck should be included if clinically indicated. If a CT scan with contrast is contraindicated (e.g., in patients with impaired renal clearance), a non-contrast CT scan of the chest may be performed along with MRI scans of the abdomen, pelvis and head. In the event a positron emission tomography (PET)/CT scanner is used for tumour assessments, the CT portion of the PET/CT must meet criteria for diagnostic quality. Clinical disease assessments by physical examination should be performed for patients with palpable/superficial lesions. Tumour measurements for each patient should be made by the same investigator or radiologist, if feasible, ideally using the same assessment technique or procedure throughout the study. Results must be reviewed by the investigator before dosing at the next cycle.

Disease status will be determined according to RECIST v1.1 (see [Appendix 5](#)) with a modified measurability definition for intracranial lesions (≥ 0.5 cm by MRI) and allowing up to five intracranial target lesions (in addition to any extracranial target lesions). Exploratory analyses of disease status will include evaluations by immune-modified RECIST (see [Appendix 6](#)), RECIST v1.1 modified by excluding any SRT lesions from the sum of largest diameters from baseline onwards (if applicable), and iRANO criteria (see [Appendix 7](#)).

Disease responses for all endpoints will be confirmed by two consecutive assessments at least four weeks apart. Tumour assessments showing disease progression must be repeated approximately four weeks later regardless of whether treatment is continued

beyond progression. If disease progression is not confirmed, the subsequent tumour assessment should occur at least four weeks later. However, post-progression assessments may be conducted sooner for patients continuing study treatment beyond progression if necessary e.g., due to clinical progression. Objective response (CR or PR) must be confirmed by repeat assessments ≥ 4 weeks after initial documentation. In the case of SD, tumour measurements must meet criteria for SD ≥ 6 weeks after initiation of study treatment.

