6.4.1 Primary Efficacy Endpoint

The primary efficacy objective is to evaluate the intracranial ORR in the BRAF^{V600} mutation-positive study cohort. Intracranial ORR is defined as the proportion of patients with a complete or partial response in their intracranial disease based on two consecutive assessments ≥ 4 weeks apart. Disease status will be determined by an IRC according to RECIST v1.1 with a modified measurability definition for intracranial lesions (≥ 0.5 cm by MRI) and allowing up to five intracranial target lesions. Data for patients with no post-baseline intracranial tumour assessment will be excluded from efficacy analyses. For intracranial response rate, a 95% Pearson-Clopper CI will be calculated and presented.

A sensitivity analysis of the primary endpoint that includes patients with unconfirmed CR or PR will also be conducted in each cohort based upon the Safety population in order to detect a potential bias with regard to the primary analysis.

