Appendix 5Response Evaluation Criteria in Solid Tumors, Version 1.1 (RECIST v1.1)

evaluations. In addition, if a lymph node lesion shrinks to a non-malignant size (short axis < 10 mm), this should be captured on the CRF as part of the assessment of non-target lesions.

RESPONSE CRITERIA

CRITERIA FOR TARGET LESIONS

Definitions of the criteria used to determine objective tumor response for target lesions are provided below:

- Complete response (CR): Disappearance of all target lesions
- Any pathological lymph nodes must have reduction in short axis to < 10 mm.
- Partial response (PR): At least a 30% decrease in the sum of diameters of all target lesions, taking as reference the baseline sum of diameters, in the absence of CR
- Progressive disease (PD): At least a 20% increase in the sum of diameters of target lesions, taking as reference the smallest sum of diameters on study (including baseline)
- In addition to the relative increase of 20%, the sum of diameters must also demonstrate an absolute increase of ≥ 5 mm.
- Stable disease (SD): Neither sufficient shrinkage to qualify for CR or PR nor sufficient increase to qualify for PD

CRITERIA FOR NON-TARGET LESIONS

Definitions of the criteria used to determine the tumor response for the group of non-target lesions are provided below. While some non-target lesions may actually be measurable, they need not be measured and instead should be assessed only qualitatively at the timepoints specified in the schedule of activities.

- CR: Disappearance of all non-target lesions and (if applicable) normalization of tumor marker level
- All lymph nodes must be non-pathological in size (< 10 mm short axis).
- Non-CR/Non-PD: Persistence of one or more non-target lesions and/or (if applicable) maintenance of tumor marker level above the normal limits
- PD: Unequivocal progression of existing non-target lesions

SPECIAL NOTES ON ASSESSMENT OF PROGRESSION OF NON-TARGET LESIONS

Patients with Measurable and Non-Measurable Disease

For patients with both measurable and non-measurable disease to achieve unequivocal progression on the basis of the non-target lesions, there must be an overall level of substantial worsening in non-target lesions in a magnitude that, even in the presence of SD or PR in target lesions, the overall tumor burden has increased sufficiently to merit discontinuation of therapy. A modest increase in the size of one or more non-target

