During the study, all target lesions and up to five measurable new lesions (lymph node and non-lymph node) should have their actual measurements recorded at each subsequent evaluation, even when very small (e.g., 2 mm). However, sometimes lesions or lymph nodes become so faint on CT scan that the radiologist may not feel comfortable assigning an exact measurement and may report them as being too small to measure. When this occurs, it is important that a value be recorded on the CRF, as follows:

- If it is the opinion of the radiologist that the lesion has likely disappeared, the measurement should be recorded as 0 mm.
- If the lesion is believed to be present and is faintly seen but too small to measure, a default value of 5 mm should be assigned and "too small to measure" should be

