### **5.3.1 Definition of Primary Endpoint**

Intracranial objective response rate (ORR) is defined as the proportion of patients with a complete or partial response in their intracranial disease based on two consecutive assessments  $\geq 4$  weeks apart. Disease status will be determined by an IRC according to RECIST v1.1 with a modified measurability definition for intracranial lesions ( $\geq 0.5$  cm by MRI) and allowing up to five intracranial target lesions.

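### The 5 mm default for a faint target equals the 5 mm minimum for brain targets, so some patients with small lesions cannot be scored PR

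*Protocol*

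**What the plan says.** Protocol 6.4.1 bases the primary endpoint on RECIST v1.1 with a "modified measurability definition for intracranial lesions (≥ 0.5 cm by MRI) and allowing up to five intracranial target lesions". SAP 5.3.1 agrees: "Disease status will be determined by an IRC according to RECIST v1.1 with a modified measurability definition for intracranial lesions". Eligibility (Protocol 4.1.1) matches: "Measurable brain metastases defined as any lesion that can be accurately measured in at least one dimension as ≥ 0.5 cm by MRI". Protocol 4.5.6 points to Appendix 5 for the criteria and names only two departures for brain disease, the "modified measurability definition for intracranial lesions" and the five-target allowance.

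Appendix 5 itself was not adapted. Its minimum target size is still "10 mm by computed tomography (CT) or magnetic resonance imaging (MRI) scan". For targets that become hard to measure it has three branches:

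- A lesion judged likely gone is recorded as 0 mm.
- A lesion the radiologist can measure is recorded at its actual size, even below 5 mm.
- Where "the lesion is believed to be present and is faintly seen but too small to measure, a default value of 5 mm" is recorded and a too-small-to-measure box is ticked.

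Appendix 6 (imRECIST) has the same third branch: "faintly seen but too small to measure, a default value of 5 mm should be assigned". PR under Appendix 5 is "At least a 30% decrease in the sum of diameters of all target lesions", relative to baseline.

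**The concern.** With a 10 mm minimum, the default is harmless: a target that fades to an unmeasurable trace always registers at least a 50% decrease. Once the minimum for brain targets drops to 5 mm, the smallest allowed baseline and the value given to a faint residual are the same number. A 5 mm lesion that fades to a trace is then recorded as unchanged.

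The order of response can also reverse. A 5 mm lesion clearly measured at 3 mm counts as a 40% decrease and PR, while a fainter residual counts as 0% and SD. The call then turns on whether the reader is willing to put a number on the residual.

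This rule decides who is a responder for the primary endpoint. It also feeds investigator intracranial ORR, overall ORR and the imRECIST ORR. None of the planned analyses would show the effect. The sensitivity analyses in SAP 5.3.3 change the population and the confirmation requirement, not the default. IRC-investigator concordance would miss it if both apply the same rule. The subgroups in SAP 5.3.4.1 do not include baseline intracranial lesion size.

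**Working it through.** **Inputs.** Brain target minimum 5 mm and up to five targets (Protocol 6.4.1, SAP 5.3.1); default 5 mm (Appendix 5); PR at a decrease of 30% or more from the baseline sum (Appendix 5); 50 evaluable patients in Cohort 2 (Protocol 6.1).

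**The plan's own figure.** Table 8 in Protocol 6.1 is reproduced by the normal approximation p ± 1.96 × √(p(1 − p)/50). At p = 0.40 the half-width is 1.96 × √(0.24/50) = 0.136, giving 26.4% to 53.6% as printed; the other four rows also match. The exact (Clopper-Pearson) interval that the plan will report for 20/50 is 26.4% to 54.8%.

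**All targets faint.** With k targets, baseline sum S and every target scored 5 mm, PR needs (S − 5k)/S ≥ 0.30. That means S/k ≥ 5/0.7 = 7.14 mm. CR is not available, because the lesion is still believed to be present.

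| Baseline diameter (mean, if several) | Scored 5 mm by default | Actually measured at 3 mm |
|---|---|---|
| 5 mm | 0%, SD | −40.0%, PR |
| 6 mm | −16.7%, SD | −50.0%, PR |
| 7 mm | −28.6%, SD | −57.1%, PR |
| 7.2 mm | −30.6%, PR | −58.3%, PR |
| 8 mm | −37.5%, PR | −62.5%, PR |
| 10 mm | −50.0%, PR | −70.0%, PR |

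**Mixed sizes.**

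- Targets of 5 and 20 mm, the first faint and the second now 14 mm: 25 to 19 mm, −24%, SD. With the first measured at 2 mm: 25 to 16 mm, −36%, PR.
- Targets of 5 and 10 mm, both faint: 15 to 10 mm, −33.3%, still PR.

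**Effect on ORR.** Each patient called SD instead of PR costs 1/50 = 2 points. The number of such patients is not in the documents. As an assumed range, suppose 20/50 are scored as responders and 0 to 5 others are affected:

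| Patients affected | ORR without the error | Exact 95% CI |
|---|---|---|
| 0 | 40% | 26.4 to 54.8 |
| 1 | 42% | 28.2 to 56.8 |
| 3 | 46% | 31.8 to 60.7 |
| 5 | 50% | 35.5 to 64.5 |

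**Effect of an alternative default of 2.5 mm (half the brain minimum).** A faint 5 mm lesion scores −50% and a faint 7 mm lesion −64.3%, both PR. Any value up to 0.7 × 5 = 3.5 mm would let a 5 mm lesion reach PR. The alternative also lowers the nadir. Five faint targets would sum to 12.5 mm, and later readings of 3.5 mm each (17.5 mm) would be +40% and +5 mm, which meets PD. Under the 5 mm default the earlier sum is 25 mm, and the same readings are not PD.

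**The case against.** A reader might infer that small brain lesions that almost vanish are generally scored as stable, and that the primary ORR is therefore understated by several points. The documents do not support that, for four reasons.

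- Appendix 5 requires the actual measurement even when it is very small, and 0 mm when the lesion has probably gone. A 5 mm lesion read at 2 or 3 mm is PR. Only a residual that is seen but cannot be measured gets the default. Targets are also chosen by longest diameter, so the largest suitable lesions must average under 7.14 mm for the all-faint case to arise.
- The primary endpoint is read by the IRC under a charter that is not among the documents and may set its own rule.
- The default rule speaks of lesions faint on CT, whereas Protocol 4.5.6 requires MRI for brain disease.
- Neither the baseline lesion sizes nor the frequency of unmeasurable residuals is given, so any estimate in points rests on assumption alone.

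These limits stand, but they do not remove the problem. The two 5 mm figures are not reconciled anywhere in the supplied text. If the CT wording means the rule does not apply to MRI, there is no instruction at all for faint brain residuals. The investigator endpoints use Appendix 5 as well, whatever the IRC charter says.

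The trial is also descriptive, with no hypothesis or decision threshold, and Table 8 half-widths are about 13 to 14 points against 2 points per affected patient. That limits the seriousness. Separately, the SAP's amendment rationale notes that excluding patients with fewer than two scans could inflate response rates, so the net direction of bias in the primary ORR is not settled by this point alone.

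**Conclusion.** The concern holds in a limited form. When every target is visible, unmeasurable and not judged gone, and the targets averaged under 7.14 mm at baseline, the written rule cannot give PR; some mixed-size patients near the 30% line can also be tipped to SD. Any error in the response call from this source lowers intracranial ORR, by 2 points per affected patient at 50 evaluable patients. The number affected is unknown and may be zero. This assumes that the IRC and investigators apply Appendix 5 as written to MRI, which the supplied documents neither confirm nor rule out. No sample size or power figure changes.

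**What to change.** - **Reading rule.** State in Appendices 5 and 6 and in the IRC reading rules how the default applies to intracranial targets with a 5 mm minimum on MRI.
- **Record its use.** Have the IRC record the too-small-to-measure flag for each target. Appendix 5 places the tick box on the case report form, and nothing supplied shows that the IRC data hold it.
- **Sensitivity analysis.** Keep the primary rule unchanged. Pre-specify in SAP 5.3.3 an analysis of intracranial ORR, for both IRC and investigator reads, that re-scores flagged intracranial targets below 5 mm, for example at 2.5 mm. Report the number of patients whose call changes.
- **Limit its use.** Do not apply the alternative value to PD, PFS, DOR or treatment decisions, because it lowers the nadir.

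The cost is a few sentences, one recorded field for the IRC and a little programming; no new scans are needed. The downside is that 2.5 mm can be generous: a 5 mm lesion that is truly near 4 mm has shrunk by 20% (SD) but would be scored as −50% (PR). That is why it belongs in a sensitivity analysis and not in the primary rule.
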